Arts-based Social Prescribing for Mental Health in Adults with Psychiatric Diagnoses. (AoP-II)

NCT ID: NCT07137572

Document date: August 23, 2025

Study Protocol

Organization's Unique Protocol ID: AoP-II

Brief Title: Arts-based Social Prescribing for Mental Health

Acronym: AoP-II

Study Type: Interventional

Official Title: Arts-based Social Prescribing for Mental Health in Adults With Psychiatric Diagnoses

Record Verification Date: August 2025

Study Start Date: September 2025, Anticipated

Primary Completion Date: January 2026, Anticipated

Study Completion Date: January 2026, Anticipated

Sponsors and Collaborators

Responsible Party, by Official Title: Sponsor

Name of the Sponsor: University Mental Health Research Institute, Athens, Greece

Oversight

U.S. FDA-regulated Drug: No

U.S. FDA-regulated Device: No

U.S. FDA IND/IDE: No

Board Status: Submitted, approved

Approval Number: UMHRI session 7/15-10-2024

Board Name: Institutional Review Board; Epitropi Vioithikis kai Deontologias) of the UMHRI

Board Affiliation: UMHRI

Board Contact Information

[contact]

Email: [contact]

Address: [name]

Study Description

Brief Summary

This is a parallel-group randomised-controlled trial aiming to assess the effect of exposure to the arts on mental health and wellbeing of community dwelling recipients of mental health care. The trial constitutes a comparison of two arms: An Art Intervention arm, hereby the Active Group (AG), versus a waitlist control arm (WL).

Detailed description

Design:

This is a randomised controlled trial with two arms: art intervention (any of the arts interventions, see below), which is hereby called Active Group (AG) vs waitlist control (WL). This is a new RCT that is based on a previous RCT performed in 2024 (NCT06361667). This trial has been approved by the Institutional Ethics Committee (Institutional Review Board; Epitropi Vioithikis kai Deontologias) of the UMHRI in Greece (UMHRI session 7/15-10-2024).

This trial will be conducted as part of the novel Arts on Prescription initiative of the Hellenic Ministry of Culture in Greece and at several Ministry-of-Culture-approved Organisations from the field of arts and culture. The University Mental Health, Neurosciences and Precision Medicine Research Institute 'COSTAS STEFANIS' (UMHRI) was commissioned by the Ministry of Culture to organize and conduct the RCT. In the beginning, an open invitation to institutions of culture and mental health has been sent. Cultural organizations presented their action plans for interventional courses. After quality control by the UMHRI and the Ministry of Culture. the following cultural organizations provided approved action plans: National Gallery - Alexandros Soutsos Museum, National Museum of Contemporary Art Athens, Athens Concert Hall Organization, Greek National Opera, Athens Conservatoire, Michael Cacoyannis Foundation, Stavros Niarchos Foundation Cultural Center (SNFCC), Nikolaos and Dolly Goulandris Foundation - Museum of Cycladic Art, Galilee Palliative Care Centre of the Holy Metropolis of Mesogaia and Lavreotiki, Archaeological Museum of Thessaloniki, Thessaloniki Concert Hall Organization, Metropolitan Organisation of Museums of Visual Arts of Thessaloniki (MOMus)", Kazantzakis Museum, Paul and Alexandra Canellopoulos Museum, National School of Dance (KSOT), Municipal Regional Theatre of Ioannina, National Theatre of Northern Greece, Drama International Short Film Festival (DISFF) Cultural Organization, and Heraklion Archaeological Museum.

AG consists of art intervention sessions that have been *a priori* developed by each cultural organization, specific to the field of each cultural organization (i.e., theatre, dance, visual arts, music, cinema). The intervention sessions have been elaborated and enhanced based on the previous experience of the NCT06361667 trial; specifically, the differences versus the NCT06361667 trial are the following: i. all Cultural Organizations are offering weekly sessions and there is no variability in the total number of sessions provided, ii. a larger sample is included in this trial to improve the precision of estimates and be able to detect smaller effect sizes (given the potential scalability and public health relevance of

the intervention, and iii. this trial includes Cultural Organizations and therefore patients beyond the metropolitan areas of Athens and Thessaloniki.

Participants will be randomly allocated to AG or WL for 12 weeks; that marks the end of the trial period. After completion of the 12-week trial, people who were included in the WL will have the opportunity to receive art on prescription by the Cultural Organizations the participated in the trial, should they wish to take this up.

Randomisation will be performed separately in each Cultural Organization and will be carried out using a computer-generated list provided centrally by SIBA Soft (Athens, Greece), an independent software and project management company.

Frequency of Measurement:

Data will be collected at baseline, including gender, age, educational level, marital status, socioeconomic characteristics, and mental health conditions. The primary and the secondary outcomes will be measured at time points:

- T0: (before the randomisation; and after informed consent and patient's sociodemographic data)
- T1: 6 weeks (after the start of the intervention for the AG group or the entry into the study for the WL group)
- T2: 12 weeks (after the start of the intervention for the AG group or the entry into the study for the WL group)

Interventional Model Description:

The duration of the RCT will be 12 weeks. The AG group will engage in different art forms (theatre, dance, visual arts, music, and cinema), whereas the WL group will remain in the waiting list.

The AG intervention will consist of sessions and/or performances in one of the five art forms: theatre, dance, visual arts, music and cinema. The number of sessions/performances will be 12 for all art forms over the duration of the trial, based on the specific features of each Cultural Organization.

The intervention activities in the AG group have been organized by each site and approved by the UMHRI and the Hellenic Ministry of Culture creating a space for 8-16 participants per activity.

The intervention consists of weekly visits over three months, featuring a guided tour followed by an art activity. All activities will include a discussion group, fostering reflection and connection, and each session will last approximately 1.5 to 2 hours. UMHRI and Ministry of Culture-approved, experienced professionals from the fields of mental health and arts, will lead the intervention sessions ensuring the safety and support of participants.

Statistical analysis model and sample size calculation

The standard practice for RCTs will be followed and a linear mixed effects model will be applied, with random intercepts to estimate the effects of treatment, time, with interaction terms for treatment (AG treatment) and time (6 and 12 weeks). The inference of interest for the study concerns the interaction term at week 12.

Assuming correlation coefficients equal to $r_{0_6_weeks} = 0.71$, $r_{0_12_weeks} = 0.65$ and $r_{6_12_weeks} = 0.69$ for the 0-6, 0-12 and 6-12 week intercorrelations, respectively, in the primary outcome values (PHQ-9), with a standard deviation of 5.60 at week 12 (numbers drawn from the results of the NCT06361667 trial) and a Cohen's d for the interaction term that is equal to 0.258 at week 12 for PHQ-9, at a type I error set at 5%, 205 participants per intervention arm would be needed for the achievement of 80% statistical power; importantly, assuming an anticipated 20% loss at follow-up rate, the total number required is 410/0.8, yielding 512 participants (256 participants by treatment arm). The power calculation was performed using the GLIMMMPSE online statistical software (<https://glimmpse.samplesizeshop.org/>)

Sensitivity analyses will be carried out, including site as a fixed/random effects factor in the models. In case of missing longitudinal data, sensitivity analyses will be performed using maximum likelihood / Last Observation Carried Forward (LOCF) approaches.

Conditions

Mental Health Issue; Anxiety Disorders; Affective Disorders; Affective Disorders, Psychotic; Psychotic disorder; Adjustment Disorder; Autism Spectrum Disorder; Mild Cognitive Impairment; Depression Disorders; Schizophrenia Disorders

Keywords

Mental Health Issue; Anxiety Disorders; Affective Disorders; Affective Psychotic Disorders; Psychotic disorders; Adjustment Disorders; Autism Spectrum Disorders; Mild Cognitive Impairment; Depression; Schizophrenia; Non-affective psychotic disorders; Psychological and behavioural factors associated with disorders or diseases classified elsewhere (ICD-10 diagnosis code F54

Primary Purpose: Other

Study Phase: N/A

Interventional Study Model: Parallel

Number of Arms: 2

Masking: None (Open Label)

Allocation: Randomized

Enrollment – Number of Participants: 512

Type: Anticipated

Arms and Interventions

Arms	Intervention
Arm Title: Active Group (AG) Arm Type: Experimental Arm Description: This arm will receive the arts intervention (any of the arts interventions).	Intervention Type: Other Intervention Name: Art Prescription Other Intervention Names: Arts (theatre, dance, visual arts, music or cinema). Intervention Description: Any of the art interventions (theatre, dance, visual arts, music or cinema)
Arm Title: Waiting list Control (WL) Arm Type: No intervention Arm Description: This arm will remain in the waiting list during the 12-week period	No intervention

Primary Outcome Measure

Outcome Measure	Measure Description	Time Frame
The Patient Health Questionnaire-9 (PHQ-9)	The Patient Health Questionnaire-9 (PHQ-9) is a questionnaire which measures depression and grade severity of symptoms in general medical and mental health settings using nine DSM-5 criteria for major depression within the last two weeks. PHQ-9 was constructed in 2001 and has been validated in Greek in 2011, using a four-point Likert-type scale. After summing all responses (0=not at all, 3=nearly every day), scores range from 0 to 27, with higher levels indicating increased	From enrollment to the end of intervention at 12 weeks

Outcome Measure	Measure Description	Time Frame
	symptom severity (0-4 no to minimal; 5-9 mild; 10-14 moderate; 15-19 moderately severe; 20-27 severe). The reliability of the PHQ-9 was excellent, with a Cronbach's alpha of 0.89 in the PHQ Primary Care Study and 0.82 in the Greek validation study.	

Secondary Outcome Measures

Outcome Measure	Measure Description	Time Frame
Generalised Anxiety Disorder Assessment (GAD-7)	The Generalised Anxiety Disorder Assessment (GAD-7) is provided to screen symptom severity for the four most common anxiety disorders (generalized anxiety disorder, panic disorder, social phobia and posttraumatic stress disorder). GAD-7 was constructed in 2006 and was validated in Greek in 2022. It consists of 7 items. The GAD-7 score is computed by assigning scores of 0, 1, 2, and 3, to the response categories of 'not at all', 'several days', 'more than half the days', and 'nearly every day', respectively, and summing together the scores for the seven questions (scores range from 0 to 21). Higher levels indicate increased anxiety. There are cut-offs for severity of anxiety as: (i) score 0-4: Minimal Anxiety; (ii) score 5-9: Mild Anxiety; (iii) score 10-14: Moderate Anxiety; (iv) score greater than 15: Severe Anxiety. The internal consistency of the GAD-7 has been excellent.	From enrollment to the end of intervention at 12 weeks
The Warwick-Edinburgh Mental Wellbeing Scale (WEMWBS)	The Warwick-Edinburgh Mental Wellbeing Scale (WEMWBS). This tool was developed in 2007, in order to measure mental wellbeing in the general population. It consists of 14 items responding using a 5-point Likert scale from 1 (never) to 5 (all the time). The overall score is calculated by summing the responses for every item without reversing none. The minimum overall score ranges from 14 to 70. Higher scores indicate increased mental wellbeing. The scale has been widely used	From enrollment to the end of intervention at 12 weeks

Outcome Measure	Measure Description	Time Frame
	
nationally and internationally for monitoring, evaluating projects and programmes and investigating the determinants of mental wellbeing. An efficient internal consistency was proven using Cronbach's alpha score which was 0.89 for the student sample and 0.91 for the general population sample. Also, test-retest reliability at one week was high (0.83). The Greek validation study showed acceptable internal consistency (Cronbach's alpha score 0.90).
	
UCLA 3-item Loneliness Scale	
The Revised UCLA Loneliness Scale-20 (UCLA-20) is a questionnaire which measures level of psychological loneliness experienced by a person. UCLA-20 was constructed in 1980 and was validated in Greek in 1992. The internal reliability of the UCLA-20 was excellent, with a Cronbach's alpha of 0.94 in the original study and 0.89 in the Greek validation study. In 2004, this long scale was shortened to 3 questions (UCLA 3-item Loneliness Scale) in order to be used in large surveys. It is using a 3-point Likert-type scale (hard ever, some of the time, often). The scores can be added together to give a range of scores from 3 to 9. Higher scores mean most lonely (worse outcome).
	From enrollment to the end of intervention at 12 weeks

Eligibility

Accepts Healthy Volunteers: No

Sex/Gender: All

Gender Based: No

Age Limits

Minimum Age: 18 years

Maximum Age: No Limit

Eligibility Criteria

Description

The study will be advertised to public and private mental health professionals across Greece, including those in public hospitals, day care centres, and non-governmental and non-profit organisations. Clinicians will then refer potential participants to the study.

Inclusion Criteria:

- Recipients of mental health care in the community, or private practice with an F-category ICD-10 diagnosis referred to the trial by their mental healthcare provider
- Age range: ≥ 18 years
- Being able to communicate effectively in order to provide answers to questionnaires that he/she/they will be asked to complete
- Being able to participate in the activity alone (unaccompanied, without a carer)
- Being able to answer the questionnaires
- Having legal capacity to consent

Exclusion Criteria:

- Current substance abuse dependence,
- Current condition posing clinical risks (e.g. acute psychosis)
- Patients that are not compliant in following their medication plans,
- Patients that are not able attend due to severe physical, cognitive or other impairments
- Patients not "affiliated" with a mental health professional therapist.

Contacts and Locations

Central Contact Person

Name: [name], PhD, FRANZCP

[contact],6

Email: [contact]

Location

The University Mental Health, Neurosciences and Precision Medicine Research Institute 'COSTAS STEFANIS' (UMHRI)

Athens 11527, Greece

Facility Contact: [name]

[contact]

E-mail: [contact]

IPD Sharing: No

Funding: Recovery and Resilience Fund European Union, Greece 2.0

Investigators

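### The arts arm is treated in groups and the waitlist is not, but the primary model and power calculation ignore this, so the standard error of the week-12 effect may be too small

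*Protocol*

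**What the plan says.** Under Interventional Model Description, each site organises its own activities, "creating a space for 8-16 participants per activity". Visits are weekly for three months, led by professionals, and "All activities will include a discussion group, fostering reflection and connection". The Detailed description says the content was "developed by each cultural organization, specific to the field of each cultural organization". The comparison arm has no such structure: "whereas the WL group will remain in the waiting list". On allocation, "Randomisation will be performed separately in each Cultural Organization", so individuals are randomised and every organization contributes to both arms.

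Under Statistical analysis model and sample size calculation, "a linear mixed effects model will be applied, with random intercepts to estimate the effects of treatment, time", with treatment-by-time interaction terms. The week-12 interaction is the target of inference. The level of the random intercepts is not named. The power inputs are three within-person correlations (0.71, 0.65, 0.69), an SD of 5.60, d = 0.258, a 5% type I error and 20% loss, and the result is that "205 participants per intervention arm would be needed for the achievement of 80% statistical power". No group size, ICC or design effect appears. Site enters only here: "Sensitivity analyses will be carried out, including site as a fixed/random effects factor in the models".

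**The concern.** This is a partially nested design. Arts-arm participants share leaders, programme content, fellow members and discussion for 12 weeks; waitlist participants share none of it. Any clustering that results arises after baseline and in one arm only.

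A model without a term for it treats arts-arm participants as independent and takes the standard error of the week-12 interaction to be smaller than it is. The confidence interval is then too narrow and the 5% test rejects too often. The point estimate is unaffected. Power is a lesser matter, because the stated contrast has some slack at 205 per arm.

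**Working it through.** **The protocol's own figure.** With independent participants, a two-sided 5% level (assumed) and the three stated correlations, a 2-df treatment-by-time test with d = 0.258 at week 12 and an assumed half effect (0.129) at week 6 needs 204 per arm and has power 0.802 at 205. So 205 can be explained without any allowance for clustering.

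**The stated target, week 12 alone (1 df).** In week-12 SD units, assuming equal SD at both visits:
- variance of change: v = 2(1 − 0.65) = 0.70
- n per arm = 2 × 0.70 × (1.96 + 0.84)² / 0.258² = 166
- at 205 per arm: SE0 = sqrt(2 × 0.70 / 205) = 0.0826; power = Φ(0.258/0.0826 − 1.96) = 0.877

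**Adding clustering in the arts arm only.** Assumptions not in the protocol:
- ρ, the ICC of the baseline-to-week-12 change within an arts group, is 0.01, 0.05 or 0.10.
- Groups enrol 12 (middle of the stated range), so m = 12 × 0.8 = 9.6 are analysed and there are 205/9.6, about 21, groups.
- Each participant stays in one group.

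Formulas:
- SE(ρ) = sqrt(v[2 + (m − 1)ρ] / 205)
- true size = 2(1 − Φ(1.96 × SE0/SE))
- power with the correct SE = Φ(0.258/SE − 1.96)

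Example, ρ = 0.05: SE = sqrt(0.70 × 2.43 / 205) = 0.0911; SE/SE0 = 1.102; size = 2(1 − Φ(1.778)) = 0.075; power = Φ(0.872) = 0.808.

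| m = 9.6 | ρ = 0.01 | ρ = 0.05 | ρ = 0.10 |
|---|---|---|---|
| SE/SE0 | 1.021 | 1.102 | 1.196 |
| SE understated by (1 − SE0/SE) | 2% | 9% | 16% |
| True size of the 5% test | 5.5% | 7.5% | 10.1% |
| Coverage of the 95% interval | 94.5% | 92.5% | 89.9% |
| Power at 205 per arm, correct SE | 86% | 81% | 74% |

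Across the stated group range:
- 8 enrolled (6.4 analysed): size 5.3% / 6.6% / 8.2%, power 87% / 83% / 79%.
- 16 enrolled (12.8 analysed): size 5.7% / 8.5% / 12.0%, power 86% / 78% / 70%.

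Power falls below 80% when 2 + (m − 1)ρ exceeds (0.258/2.80)² × 205/0.70 = 2.48, that is at ρ above about 0.090, 0.056 and 0.041 for groups of 8, 12 and 16 enrolled.

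**Does the site analysis help?** Both arms share an organization's intercept, and it is constant over time, so with complete data it cancels from the treatment-by-time interaction. The same is true of a time-constant random intercept at any level. A simulation of change scores (21 arts groups of 10, one per site) gave site more credit than that by letting site fixed effects act on the change itself. Size at ρ = 0.01 / 0.05 / 0.10:
- unadjusted: 6.1% / 7.6% / 10.0%
- site-adjusted: 6.1% / 7.8% / 10.4%
- arts-group means against individual waitlist participants, approximate t with 40 df: 5.1% / 4.6% / 4.4%

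Site adjustment leaves the inflation in place; an analysis that respects the arts groups removes it.

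**The case against.** - **A SAP may exist.** It could add a group term. But the protocol already states the primary model, its target and the place of site, and that model omits a dependence the intervention creates.
- **Site could be entered differently.** The wording does not confine site to a common intercept. The 19 listed organizations and 256 arts-arm participants give about 13.5 each, so group and site may nearly coincide, and a site-by-arm-by-time effect would answer the point. That stands, but the protocol does not specify one, and site is confined to sensitivity analyses.
- **Fixed or random programmes.** If only these approved programmes are of interest, differences in effect between them need not enter the SE. The Detailed description cites scalability, which points to wider inference, and chance events shared within a group matter either way. It is also true that if the intervention moves nobody's outcome in any group, no clustering arises and the test keeps its size.
- **The ICC is assumed.** This stands. At 0.10 the between-group SD is sqrt(0.10 × 0.70) × 5.60 = 1.48 PHQ-9 points, slightly more than the whole assumed effect (0.258 × 5.60 = 1.44), so 0.10 is a demanding value. At 0.05 it is 1.05 points.
- **A conservative offset.** Site-by-time variance common to both arms cancels from the contrast but stays in the unadjusted SE. If it is 5% of the change variance (assumed), size becomes 4.9% / 6.9% / 9.5%. This removes the problem at 0.01 and only reduces it above that.
- **The basis of calculation.** The figures are for a change-score test; a random-intercept model imposes one common correlation and has a somewhat different SE. Power also depends on the starting point: calibrated to the protocol's 80% at 205, with 12 analysed per group, it is 78% / 70% / 61%. The power thresholds above are therefore illustrative. The SE ratios do not depend on this calibration.

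**Conclusion.** The concern holds. The primary model and the power calculation leave out clustering that the design can create in one arm. With any positive ICC, and no offset from shared site-by-time variance, the interval for the primary effect is too narrow and the test exceeds 5%. At an ICC of 0.05 the true size is about 7.5% (6.6% to 8.5% over the stated group sizes); at 0.01 the effect is negligible. These sizes rest on the assumed ICC, the change-score approximation and stable group membership, so confidence in the magnitude is medium. The effect estimate is not biased. On the 1-df week-12 contrast, power stays above 80% under modest clustering. The plan should be corrected before analysis.

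**What to change.** - Record the activity group of every arts-arm participant. Without it the correction may not be recoverable later.
- In the primary model, add a group random effect acting on the post-baseline visits of the arts arm only, with waitlist participants as singletons. If each organization runs one group, a site-by-arm-by-time random effect is equivalent.
- Use Satterthwaite or Kenward-Roger degrees of freedom, since there may be only about 21 groups.
- Report power at 205 per arm over a stated range of ICC and group size. Do not enrol more on this account: a larger sample does not repair a wrong standard error.

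The cost is analysis wording and one recorded variable. The 95% interval widens somewhat: the half-width is 1.96 × 0.0826 × 5.60 = 0.91 PHQ-9 points under independence and, multiplied by 1.021 / 1.102 / 1.196, becomes 0.93 / 1.00 / 1.08 at ICC 0.01 / 0.05 / 0.10. Stated power is less favourable, and small-sample degrees of freedom (about 69 / 56 / 47) lower it by a further 1 to 2 points, to 85.4% / 79.5% / 72.5%.

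### The primary PHQ-9 contrast subtracts a pre-randomisation T0 difference; treating T0 as a baseline would cut its variance by about 15% (T0 SD assumed) with no new data

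*Protocol*

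**What the plan says.** All of this is in the Protocol's Detailed description.

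- **Model** (Statistical analysis model and sample size calculation): "a linear mixed effects model will be applied, with random intercepts to estimate the effects of treatment, time, with interaction terms for treatment". The interactions are spelled out as "interaction terms for treatment (AG treatment) and time (6 and 12 weeks").
- **Primary inference** (same section): "The inference of interest for the study concerns the interaction term at week 12".
- **Timing** (Frequency of Measurement): "The primary and the secondary outcomes will be measured at time points" T0, T1 (6 weeks) and T2 (12 weeks). The first is described as "T0: (before the randomisation; and after informed consent".
- **Planning values** (statistical section): PHQ-9 correlations of 0.71 (0-6 weeks), 0.65 (0-12) and 0.69 (6-12), "with a standard deviation of 5.60 at week 12", and 205 per arm, raised to 256 per arm "assuming an anticipated 20% loss at follow-up rate".

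No baseline covariate and no common T0 mean is stated. The only additions are sensitivity analyses for site and for missing data.

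**The concern.** A treatment effect together with interactions at both week 6 and week 12 can be estimated only if there is a third, reference time. That time is T0. The correlations with T0 are also listed among the primary outcome values. The treatment term is then the arm difference at T0, and the week-12 interaction is the arm difference in change from T0. This reading is an inference, because the Protocol does not write the model out, but the structure leaves little room for another.

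T0 is measured before randomisation, so the true arm difference there is zero in expectation. The named contrast estimates it anyway and subtracts the estimate with a coefficient of 1, whatever the correlation between T0 and week 12. A model that uses T0 as a baseline targets the same effect and subtracts only what the correlation supports.

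What is at stake is precision, not validity. The Design section gives better precision, and the ability to find smaller effects, as a reason for the larger sample. The data needed for further precision are already being collected.

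**Working it through.** **Inputs.** From the Protocol: correlations 0.71, 0.65 and 0.69; week-12 SD 5.60; 256 per arm at T0 and 205 at week 12. Assumed: T0 SD s0 = 5.60, range 5.0 to 6.2, because only the week-12 SD is given; loss missing at random; likelihood-based analysis. The week-6 SD is not given either, but varying it from 5.0 to 6.2 changes no result.

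**The plan's own figure.** The stated 205 per arm is matched (204) by a 2-df treatment-by-time test with equal SDs, d = 0.258 scaled on the week-12 SD, and an assumed week-6 effect of half the week-12 effect. The 1-df week-12 contrast on the same scaling needs 166. The total is 410/0.8 = 512.5, stated as 512. Since the scaling of d is not stated, I claim no power figure. The variance comparison below does not use d.

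**Complete data.** Per-participant variance of each contrast:

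- change from T0: s0² + 5.60² − 2 × 0.65 × s0 × 5.60 = 21.95 at s0 = 5.60
- baseline-adjusted: 5.60² × (1 − 0.65²) = 18.11
- reduction: 1 − 18.11/21.95 = 17.5% (9.3% at s0 = 5.0; 26.6% at s0 = 6.2)

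In 20,000 simulated trials of 205 per arm with equal SDs, the empirical reduction was 17.9%.

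**Planned 20% loss.** The mixed model recovers part of the gap from the T0 values of dropouts. If all loss comes before week 6:

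- common T0 mean: 2 × 18.11/205 = 0.1767
- free T0 means: 0.1767 + 2 × (s0 − 0.65 × 5.60)²/256 = 0.1767 + 2 × 1.96²/256 = 0.1767 + 0.0300 = 0.2067

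Generalised least squares with all three correlations covers the cases where some of the 51 dropouts per arm have a week-6 value:

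| Dropouts per arm with week 6 | Free T0 means | Common T0 mean | Reduction at s0 = 5.60 |
|---|---|---|---|
| 0 | 0.2067 | 0.1767 | 14.5% |
| 26 | 0.2031 | 0.1731 | 14.8% |
| 51 | 0.2003 | 0.1703 | 15.0% |

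At s0 = 5.0 the reduction is 7.6-7.8%; at s0 = 6.2 it is 22.5-23.1%. With a compound-symmetry (random-intercept) weighting in both models and s0 = 5.60 it is 14.4-14.8%. The gain is zero only at s0 = 0.65 × 5.60 = 3.64.

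**In PHQ-9 points.** The 95% CI half-width falls from 1.96 × √0.2031 = 0.88 to 1.96 × √0.1731 = 0.82.

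**In participants.** 1/(1 − 0.148) = 1.174, and 0.174 × 512 = 89. Over 7.6% to 23.1% the range is about 42 to 154.

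**Clustering.** Activities are planned as "creating a space for 8-16 participants per activity". As an approximation, add ICC × (m − 1) × 5.60²/205 to both variances, for the active arm only, with an assumed ICC. With 26 dropouts per arm having week 6 and s0 = 5.60:

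| ICC | m | Added variance | Reduction |
|---|---|---|---|
| 0.02 | 8 | 0.0214 | 0.0300/0.2245 = 13.4% |
| 0.02 | 12 | 0.0337 | 12.7% |
| 0.05 | 12 | 0.0841 | 10.4% |
| 0.05 | 16 | 0.1147 | 9.4% |

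Combining clustering with the T0 SD range gives 4.8% at the low end (s0 = 5.0, ICC 0.05, m = 16: 0.0144/0.3024) and 21% at the high end (s0 = 6.2, ICC 0.02, m = 8: 0.0512/0.2459).

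**A remedy that does nothing.** In three simulated complete data sets, T0 PHQ-9 was added as a covariate while T0 stayed an outcome with its own arm effect. The week-12 interaction did not change (for example −1.0931 with SE 0.4353, with and without the covariate). The covariate shifts all three of a participant's fitted values equally, so it cannot alter a within-participant change.

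**The case against.** The strongest reply is that nothing here is wrong. The contrast is unbiased, the sample size is written for the interaction, and baseline covariates and covariance structure often belong in a SAP, which is not at hand. On one scaling of d (week-12 SD) the week-12 contrast needs only 166 per arm, so the plan may already have slack. The T0 SD and the ICC are assumed, and in outcome units the central gain is about 0.07 points of CI half-width on a 0-27 scale.

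Much of this stands, and it limits the point to efficiency. The range must include clustering: the floor is then about 5%, worth some 25 participants, not the 7.6% and 42 obtained without it. The aim of better precision in the Design section concerns sample size rather than the estimator, so no planned precision is lost; some that is available goes unused.

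The appeal to the SAP does not stand. The Protocol itself fixes the model terms and names the contrast for inference. A SAP that adjusted for baseline would depart from that text.

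**Conclusion.** The point holds as a missed gain in efficiency, not as an error of validity. With the Protocol's correlations and planned loss, and a T0 SD assumed equal to 5.60, using T0 as a baseline cuts the variance of the week-12 effect by about 15%. The range is 7.6% to 23.1% for T0 SDs of 5.0 to 6.2, and about 5% to 21% once assumed clustering is added. It rests on reading T0 as the reference time with its own arm effect, and on missing-at-random loss analysed by likelihood. The change should be made; confidence in its exact size is medium.

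**What to change.** In the statistical section, replace the primary PHQ-9 model with one of the following, and name the week-12 arm difference as the primary estimate:

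- **(a)** T0, week 6 and week 12 as outcomes, a common T0 mean for both arms, and an unstructured 3×3 covariance; or
- **(b)** weeks 6 and 12 as outcomes, T0 PHQ-9 and T0-by-time as covariates, and an unstructured 2×2 covariance.

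Do not simply add T0 PHQ-9 as a covariate to the present model.

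The cost is wording: six covariance parameters under (a) or three under (b), against two for random intercepts with independent residuals. Option (a) uses all 512 participants. Option (b) uses about 410 to 512, depending on how many dropouts have a week-6 value, with the same week-12 variance. The sentences that tie the inference and the effect size to the interaction need restating to match; 512 and the visit schedule are unaffected. The change should be made before outcome data are seen.

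An unstructured covariance has one conditional side benefit. Random intercepts with independent residuals and model-based SEs, neither of which the Protocol states, would give an SE about 5% too small: the mean correlation is 0.683, and √(0.3167/0.35) = 0.951.
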